1.3.10. Plasma levels of C1M are increased in human IPF subjects

Collagen degradation products are generated by proteolytic cleavage of ECM by matrix metalloproteinases (MMPs). Circulating concentrations of collagen digest fragments are reflective of ECM turnover, and several are prognostic of disease activity in IPF (16). C1M, which is a product of collagen 1 degradation by MMP-2/9/13, had the most favorable operating characteristics for prediction of IPF patient outcomes (16). Baseline C1M serum concentrations discriminated IPF vs. normal subjects (p = 0.001), (Fig. 9A), and these were also significantly higher in patients with progressive IPF compared to patients with stable disease (p=0.012). Longitudinal rates of later increases in C1M levels from baseline values were also predictive of mortality (Fig. 9B).

[figure not shown]

Figure 9: C1M is increased in IPF patient plasma. Plasma from IPF and healthy control subjects were analyzed by ELISA. A) Concentrations of C1M were significantly higher at baseline in IPF subjects (closed squares) than in healthy control subjects (closed circles). B) Mortality risk is greater in IPF subjects with increasing C1M concentrations relative to those with stable or falling concentrations. Values represent mean \pm SEM. Figures from (16).

1.3.11. Summary of Non-Clinical Studies with GKT137831

A broad range of *in vitro* and *in vivo* pharmacology studies have been conducted to support the use of GKT137831 in several indications. Detailed summaries for all studies are given in Section 4.1. GKT137831 selectively inhibits human isolated NOX4 (K_i 0.09 μ M) and NOX1 (K_i 0.15 μ M) but is considerably less active at inhibiting isolated human NOX2 (K_i 2.13 μ M), NOX3 (K_i 0.36 μ M) and NOX5 (K_i 0.33 μ M). This selectivity against NOX2 means that GKT137831 does not compromise phagocyte function. Moreover, GKT137831 was inactive against the non-NADPH oxidase flavoprotein xanthine oxidase, and inhibited glucose oxidase with an IC_{50} of 5.7 μ M, indicating selective inhibition of ROS generation via the NADPH oxidase pathway. Meanwhile, GKT137831 reduced DPPH with an IC_{50} of 20 μ M, suggesting that GKT137831 is a weak electron donor, and therefore has weak antioxidant activity. Investigation of potential effects against a broad range of receptors and enzymes confirmed that GKT137831 demonstrated no significant off-target binding, except for human recombinant 15-lipoxygenase-2 (IC_{50} 0.26). However, review of the literature suggests this inhibitory activity does not represent a safety concern.

Similarly, a literature review on the effect of gene deletion of NOX isoforms indicated that no basal phenotype has been associated with NOX1 or NOX4 gene deletion in mice. Specifically, there are no reported defects in fertility, embryonic development, life span, animal behavior or breeding. These observations did not identify potential safety concerns related to chronic inhibition of NOX1 and/or NOX4.

GKT137831 and GKT138184 (the major active metabolite) have limited selectivity (about two-fold) against the human NOX5 isoform. NOX5 is not present in rodent genomes and as a consequence there is scarce information about the function of this isoform (33). The NOX5 gene is found in other mammals such as dog or human and has been reported to be expressed in spleen, testis, fetal tissues, pancreas, atherosclerotic coronary arteries, prostate and prostate adenocarcinoma (34). The understanding of NOX5 function is still limited but there is some evidence for functional NOX5 in spermatocytes and for a role of ROS in sperm maturation and function and therefore these parameters were investigated in the chronic dog toxicology studies conducted with GKT137831. There were no treatment related effects following GKT137831 administration on sperm motility, mortality or morphology at any dose tested confirming a lack of adverse effects related to NOX5 inhibition.

Overall, there are no observations from the available literature to indicate safety concerns associated with chronic pharmacological inhibition of NOX1, NOX4 and NOX5.

In *in vitro* studies in isolated cells including primary human hepatic stellate cells, GKT137831 was shown to attenuate the induction of multiple fibrogenic pathways including TGF- β 1, PDGF, TLR4, Hedgehog, and angiotensin 2. Specifically, GKT137831 markedly reduced the induction of markers of myofibroblast activation including α SMA, fibronectin, and pro-collagen 1 (35).

In addition, GKT137831 has shown potent anti-inflammatory effects including reduced expression of adhesion molecules, cytokines, and chemokines. These effects were observed in human podocytes (36-38), primary human hepatic stellate cells (35, 39), macrophages, human endothelial cells (40, 41), and in rat retinal microglial and Müller cells (42).

These direct anti-inflammatory and anti-fibrogenic effects translated in anti-inflammatory and anti-fibrotic activity in multiple *in vivo* models of liver fibrosis. Specifically, GKT137831 attenuated the development of liver fibrosis induced by experimental cholestasis (bile duct ligation and MDR2^{-/-} mouse models, GKT internal study GSN000262). GKT137831 also prevented liver inflammation and fibrosis in models of NASH (STAM, GKT internal study GSN000172 and fast food diet models) and in toxic hepatitis (CCL4 induced liver injury) (43). Reduced *in vivo* fibrogenesis was associated with a marked reduction in markers of myofibroblast activation. In addition, GKT137831 prevented the induction of adhesion molecules, cytokines, and chemokines. These effects on innate immunity resulted in a profound reduction of macrophage infiltration.

These *in vitro* and *in vivo* effects achieved by GKT137831 were consistent with NOX1 and/or NOX4 gene deletion and/or gene silencing. Importantly, recent studies have shown that the expression of NOX1 and/or NOX4 is consistently induced in the target organ of patients with IPF, NASH, SSc, and cirrhosis. Accordingly, NOX1/4 inhibition with GKT137831 has the potential to achieve anti-inflammatory and anti-fibrotic activity in these patients.

In addition, GKT137831 was shown to prevent lung fibrosis in the bleomycin model of IPF. In contrast to the spontaneously reversible fibrosis induced in young mice, bleomycin causes irreversible fibrosis in aged mice. GKT137831 was able to reverse lung fibrosis in young and aged mice (32). Importantly, GKT137831 also improved survival in aged mice. In these aged mice, GKT137831 again prevented the activation and persistence of lung myofibroblasts, and facilitated their clearance through apoptosis. This data is consistent with results obtained in mice lacking NOX4, who show protection in the bleomycin model. NOX4 over-expression in lung tissue of IPF patients has been reported by several groups, suggesting that NOX1/4 inhibition with GKT137831 may delay or reverse fibrotic lung remodeling in these patients.

Altogether, the available pre-clinical evidence in multiple models indicates that GKT137831 exerts its direct anti-fibrogenic effects through the downregulation of multiple fibrogenic and inflammatory pathways.

A separate set of animal pharmacology studies indicated that GKT137831 reduces the severity of several diabetic complications. In diabetes, a number of factors induce the expression and activity of NOX1 and/or NOX4. These factors include hyperglycemia itself, as well as insulin, angiotensin 2, aldosterone, advanced glycation end products, and multiple pro-inflammatory and growth factors. Studies in murine models of diabetic kidney disease demonstrated that GKT137831 reduces podocyte loss, glomerular and interstitial fibrosis, as well as inflammation and macrophage infiltration. These results were obtained in the Akita (37), OVE26 (36), and STZ/ApoE^{-/-} mice (40,44,45). Reduced inflammation and fibrosis were associated with reduced albuminuria, a highly validated marker of disease progression in man.

These effects were also associated with a commensurate reduction in renal NADPH oxidase activity and ROS production and with improvements in glomerular structure. In the OVE26 model GKT137831 showed benefit at 10 and 40 mg/kg/day. In addition, GKT137831 (60 mg/kg/day by gavage for 10 weeks) significantly reduced atherosclerotic plaque formation in diabetic (streptozotocin-induced) ApoE^{-/-} mice compared to controls. This finding was associated with reduced nitrotyrosine and 4-HNE staining and reduced expression of VCAM-1, MCP-1, TGF- β and macrophage infiltration whilst, upregulation of CTGF, collagen IV and fibronectin was also reduced. In these models of nephropathy and atherosclerosis in diabetic ApoE^{-/-} mice, GKT137831 was as effective as NOX1 and NOX4 gene deletion, respectively. These preclinical

studies, sponsored by the Juvenile Diabetes Research Foundation, supported the initial clinical investigation of GKT137831 in patients with diabetic kidney disease.

Safety pharmacology studies demonstrated that there were no effects on general activity, behavior or respiratory parameters at doses up to 1000 mg/kg of GKT137831 when administered orally. Minimal dose-related effects on hERG currents were recorded with a reduction of ~20% at 300 μ M with GKT137831 or major active metabolite GKT138184. In addition GKT137831 was found to be a weak inhibitor (IC_{50} = 78.8 μ M) of the cardiac I_{Ks} channel while the metabolite, GKT 138184 has no activity on this channel at 100 μ M. GKT137831 and GKT138184 have no significant inhibitory activity on the I_{Kr} cardiac ion channel at 300 μ M and no activity on I_{Na} and I_{Ca} channels at 100 μ M. Overall, review of the ECG data from the safety pharmacology and toxicology studies did not provide sufficient information that GKT137831 could prolong QTc or QT_{CF} in a way that indicated a definite risk to humans.

The non-clinical pharmacokinetics (PK) and absorption, distribution, metabolism and excretion (ADME) of GKT137831 have been investigated *in vivo* in mouse, hamster, rat and dog, and in animal and human *in vitro* preparations. GKT137831 is a rapidly and extensively orally absorbed compound. In rats and dogs, it has moderately low clearance and a volume of distribution approximately similar to that of extracellular fluid and elimination predominates in feces rather than urine.

Significant amounts of the major phase 1 active metabolite GKT138184 have been quantified in animal plasma after oral dosing. The phase 1 metabolism of GKT137831 is likely to be mediated mainly by CYP3A4, and GKT137831 showed the potential to inhibit and induce CYP3A4 *in vitro*. A human drug interaction study indicated that GKT137831 is a weak inhibitor of CYP3A4 although the modest increase in the exposure of midazolam and its metabolites upon repeat dosing of GKT137831 may be due to a combination of mechanisms.

Initial *in vitro* studies indicating that GKT137831 may also be an inhibitor of BSEP were not confirmed in later repeated studies. In addition, in a specific Phase 1 study the effects of GKT137831 on bile acids were studied and there were no signs of cholestasis (i.e. no change in plasma levels of alkaline phosphatase, bilirubin, and bile acids). It is therefore considered unlikely that treatment with GKT137831 will cause cholestatic liver injury.

GKT137831 has undergone a comprehensive toxicology testing program which has demonstrated that there is no genotoxicity with either the parent or the active metabolites. In chronic studies in rats and dogs the potential toxicity of GKT137831 following up to 6 and 9 months of daily oral dosing, respectively, was explored. The NOAEL in rats was established at 1000 mg/kg/day, the highest dose tested and findings included minimal or slight decreases in red blood cells and slight increases in platelets, modest increases in total plasma bilirubin and a small increase above control in the incidence of foamy macrophages in the lung which was of minimal severity grading. No such difference between treated and control animals was observed in animals subjected to a 5-week treatment free period after 6 months of dosing and these effects were thus not considered of toxicological significance.

The dog was the most sensitive species and the NOAEL was established at 150 mg/kg/day in the 26-Week study. Treatment related effects in the dog studies were confined to ECG changes, hypothyroidism, and hematology parameters/bone marrow abnormalities. Changes in liver function tests were generally considered to be of minimal severity, reversible led to no liver pathologies and are consequently not considered to be of toxicological relevance. In the 28-Day study, QTc(F) prolongation was observed in high dose dogs (1000 mg/kg) and there was a single animal with an AV-block. The QTc prolongation was observed at both measurement times (Day 1 and Day 23) but the increase at the Day 23 reading was limited and seemed to affect only 2/6 treated high dose animals. Although there were no such ECG alterations observed in the 13-

Week study, measurements in high dose dogs taken at Week 1 and 4 of the 26-Week study (animals still on 500 mg/kg/day) showed QTc (VdeW) increases of up to 20 msec. There were no QTc prolongation observed after the dose reduction to 300 mg/kg/day at week 13 and 26. The absence of any clear treatment-related ECG alterations at both the NOAEL of 150 mg/kg/day and the HTD (Highest Tolerated Dose) of 300 mg/kg/day in the 26-Week dog study and in already conducted clinical trials suggest that any such liability will not compromise patient safety in early stage clinical studies. Effects on bone marrow were seen at 500 mg/kg/day, the highest dose tested in the 26-Week study and in one animal resulted in a severe non-regenerative anemia which leads to euthanasia. Effects were restricted to the erythroid lineage and were preceded by a marked reduction in reticulocytes indicating the potential to monitor any potential effect in the clinic.

Exposure (AUC) in the 39-week dog studies was generally rather lower than the same dose/occasion in the 26-week dog study, however the C_{max} values were generally comparable, suggesting a possible reduced impact on AUC of secondary plasma peaks in the 39-week study.

Mild increases in plasma and urinary bilirubin were observed in this study but in the absence of related histological changes these effects were not considered significant. There was no evidence of any changes in hematology parameters and no effects on cardiovascular function.

Segment 2 embryo-fetal toxicology studies have been conducted in rat and rabbit. The NOAEL for embryo toxicity in both species is generally higher than the NOAEL defined from the general chronic toxicity studies.

Overall, this body of non-clinical data suggests that NOX1/4 inhibition with GKT137831 may represent an attractive therapeutic strategy for a broad range of fibrotic disorders.

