	
15) Systemically administered potent CYP3A4 inhibitors or inducers are prohibited during the 24-week treatment period.
 
Inhibitors include: boceprevir, cobicistat, conivaptan, ritonavir, itraconazole, ketoconazole, telaprevir, troleandomycin, voriconazole, clarithromycin, diltiazem, idelalisib, nefazodone, nelfinavir.
 
Inducers include carbamazepine, enzalutamide, mitotane, phenytoin, rifampin.
 
See also: https://www.fda.gov/drugs/drug-interactions-labeling/drug-development-and-drug-interactions-table-substrates-inhibitors-and-inducers#table3-2

Study Endpoints:	
 • Primary efficacy endpoint: The primary efficacy endpoint is change in plasma o,o'-dityrosine, as determined by mass spectroscopy, from baseline to Week 24. • Secondary efficacy endpoints: Secondary efficacy endpoints are: (a) collagen degradation products, (e.g., C1M), measured in sera by ELISA; (b) forced vital capacity (FVC); and (c) six-minute walk distance (6MWD) comparing baseline to values at 24 weeks.
	
 • Safety: Adverse events (AEs) that occur anytime during the duration of the trial. Clinical laboratory evaluations will occur at Screening, baseline/Day 1 and Weeks 6, 12, 18, and 24. Urinalysis will be performed at Screening, baseline/Day 1 and Weeks 6, 12, 18, and 24. Pulse rate, SBP and DBP are recorded at Screening, baseline/Day 1 and Weeks 6, 12, 18, and 24. Body weight at Screening, baseline/Day 1 and Weeks 6, 12, 18, and 24. 12-lead ECG at Screening, baseline/Day 1 and Weeks 6, 12, 18, and 24.
	
 • Pharmacokinetics (PK): Plasma concentrations of GKT137831 and its main phase 1 metabolite, GKT138184. The plasma concentrations will be subjected to population PK analysis to estimate population PK parameters such as clearance and volume of distribution and associated inter-individual variability (IIV), and to determine predictors of IIV. PK-PD analysis will be carried out using the primary endpoint and selected secondary endpoints in order to explore any potential PK-PD relationships.

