2.6.1 Variances

A variance of 5 days will be allowed for the telephone contacts to account for weekends or holidays. A variance of 10 days will be allowed for each outpatient follow-up visit for similar reasons, as well as potential logistic/transportation problems. If subjects are hospitalized at the time of scheduled assessments, an identical evaluation and procedures will be performed (as feasible):

The schedule for patient assessment and data collection is outlined as follows.

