2.6.4 Follow-up monitoring (see Table 1 and Table 2)

Day 14 (2nd week):

- Telephone call (if outpatient, or personal visit if an inpatient) to assess status (brief assessment of symptoms, and a review of medical or surgical histories).
- AE assessment

Day 28 (4th week):

- Telephone call (if outpatient, or personal visit if an inpatient) to assess status (brief assessment of symptoms, and a review of medical or surgical histories).
- AE assessment

Day 42 (6th week):

- Physical exam and interval history assessment to include vital signs and blood pressure.
- Safety tests to include: EKG, CBC, CMP, TFT, LFT, pregnancy test, either urine or blood (if applicable).
- Venous blood by phlebotomy (a maximum of 34 ml) will be obtained, locally processed and stored frozen, for later batch shipment (while frozen) to the CCC.
- Medication review (including review of drug compliance diary)
- AE assessment.
- PK samples (2 ml each) taken upon arrival in clinic and just prior to departure from clinic

Day 56 (8th week):

- Telephone call (if outpatient, or personal visit if an inpatient) to assess status (brief assessment of symptoms, and a review of medical or surgical histories).
- AE assessment

Day 70 (10th week):

- Telephone call (if outpatient, or personal visit if an inpatient) to assess status (brief assessment of symptoms, and a review of medical or surgical histories).
- AE assessment

Day 84 (12th week):

- Physical exam and interval history assessment to include vital signs and blood pressure.
- Safety tests to include: EKG, CBC, CMP, TFT, LFT, pregnancy test, either urine or blood (if applicable),
- Venous blood by phlebotomy (a maximum of 34 ml) will be obtained, locally processed and stored frozen, for later batch shipment (while frozen) to the CCC.
- Medication review (including review of drug compliance diary)
- AE assessment.
- PK samples (2 ml) taken upon arrival in clinic and just prior to departure from clinic

Day 98 (14th week):

- Telephone call (if outpatient, or personal visit if an inpatient) to assess status (brief assessment of symptoms, and a review of medical or surgical histories).
- AE assessment

Day 112 (16th week):

- Telephone call (if outpatient, or personal visit if an inpatient) to assess status (brief assessment of symptoms, and a review of medical or surgical histories).
- AE assessment

Day 126 (18th week):

- Physical exam and interval history assessment to include vital signs and blood pressure.

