*Safety assessments include electrocardiogram (EKG), complete blood count (CBC) with platelets (plts), basic metabolic panel (BMP) with glucose, BUN, creatinine, blood pregnancy test, if applicable (Section 5.7.3.1), liver function tests (LFT) with albumin, bilirubin (total), transaminases, and thyroid function tests (TFT) with thyroid stimulating hormone (TSH) and thyroxine (T4). These assessments can be combined during screening and baseline visits as long as they are completed within 30 days of randomization and start of drug treatment. ** if applicable (see Section 5.7.3.1). In addition to the blood pregnancy test during screening, a urine (or blood) pregnancy test must be performed on the day that therapy starts. Blood tests can also substitute for urine tests at weeks, 6,12,18,24.

Table 2. PHONE CONTACTS

Weeks:	2	4	8	10	14	16	20	22	28
Phone contact	x	x	x	x	x	x	x	x	x

Subjects will be contacted by the study coordinators at these times to assess for symptoms potentially related to adverse effects of medications, review of medication changes, and interval medical or surgical histories including emergency or physician office visits.

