2.8.4 Pharmacokinetics Analyses

Plasma concentrations of GKT137831 and its main phase 1 metabolite, GKT138184 will be analyzed in plasma specimens obtained at weeks 6 and 12 of the drug therapy. The plasma concentrations will be subjected to population PK analysis to estimate population PK parameters such as clearance and volume of distribution and associated inter-individual variability (IIV), and to determine predictors of IIV. The sparse PK data from this study will be integrated into a population PK model using nonlinear mixed-effects modeling. In addition, PK-PD analysis will be carried out using the primary endpoint and selected secondary endpoints in order to explore any potential PK- PD relationships.

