5.7.2. General Measures to Reduce Risks of Experimental Intervention:

Despite the documented safety profile of GKT137831 in other human trials (see Section 5.1.2.), the study design emphasizes protecting patients against risk. General measures adopted to mitigate potential risks include:

- 1) Involvement by trained staff / investigators with experience in the administration of experimental agents
- 2) Prior human experience with the study medication in other conditions
- 3) Exclusion of patients with serious comorbidities or other potentially life-threatening problems.
- 4) Continuous monitoring by an independent DSMB

5.7.3 Specific Experimental Risk Mitigations:

5.7.3.1. Procedures to Reduce Risks of Study Drug Administration:

Although apparently safe in humans, several conservative safety measures have been implemented in this trial, singularly focusing on toxicity signals seen in preclinical dog studies. Thus, potential participants with preexistent hematological, cardiac, liver, thyroid, or renal abnormalities that could conceivably increase risks with GKT137831 will be excluded from this trial. The initial screening assessment will accordingly include the following procedures:

- Detailed medical histories.
- Physical exams to include vital signs and blood pressure.
- Laboratory evaluations, to detect safety-related exclusion criteria, include: electrocardiograms (EKG), complete blood counts (CBC), comprehensive metabolic panels (CMP), thyroid function tests (TFT), liver function tests (LFT), blood pregnancy (if applicable- see following section), and FSH (if applicable).
- Findings of laboratory abnormalities, at screening or at any subsequent assessment, irrespective of study participation or causality, that are clinically significant in the judgement of the local principle investigator will be communicated to the participant and, at their request, to

that participant's physician.

Conservative **exclusion criteria** that will further minimize potential for toxicities **include**:

A history of malignancy, excluding basal or squamous cell skin cancer and low-risk prostate cancer, the latter defined as stage T1 or T2a, with prostate specific antigen <10 ng/dl. NOX inhibition is not known to promote cancer, and these criteria are within current guidelines.

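### ECGs and PK samples share the Week 6 and Week 12 visits but are not timed to each other, and QTc is not named in the PK-PD analysis, so a small QTc effect (about 5 to 7.5 ms) may be missed although data for a sharper test are already collected

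*Combined protocol and SAP*

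**What the plan says.** **Non-clinical signal (Section 1.3.11).** ECG changes are listed among the treatment-related dog effects. In the 28-day study at 1000 mg/kg: "The QTc prolongation was observed at both measurement times (Day 1 and Day 23) but the increase at the Day 23 reading was limited". In high-dose dogs, readings at "Week 1 and 4 of the 26-Week study (animals still on 500 mg/kg/day) showed QTc (VdeW) increases of up to 20 msec". No prolongation was seen in the 13-week study, or at 300 mg/kg/day after the dose was reduced. No clear ECG change was seen at the 150 mg/kg/day NOAEL.

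**Human data (Section 1.3.12).** Phase 1 had no clinically significant ECG finding. The diabetic kidney disease trial, at up to 200 mg BID, had no cardiac conduction signal. No ECG result is given for the PBC trial, which tested the 400 mg BID dose used here.

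**Aim and stated focus.** Aim 3 (Section 1.2) includes ECG abnormalities. Section 5.7.3.1 describes the safety measures as "singularly focusing on toxicity signals seen in preclinical dog studies".

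**Schedule.** The Synopsis lists "12-lead ECG at Screening, baseline/Day 1 and Weeks 6, 12, 18, and 24". The Table 1 footnote adds: "These assessments can be combined during screening and baseline visits". Weeks 2 and 4 are telephone contacts (Section 2.6.4, Table 2). Section 2.6.1 states: "A variance of 10 days will be allowed for each outpatient follow-up visit".

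**PK and PK-PD.** At Week 6, and likewise at Week 12, Section 2.6.4 has "PK samples (2 ml each) taken upon arrival in clinic and just prior to departure from clinic". The ECG at those visits appears only in the list of safety tests, with no time relative to dose or draw. Section 2.8.4 says "PK-PD analysis will be carried out using the primary endpoint and selected secondary endpoints". Section 2.8 describes no QTc analysis.

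**The concern.** The trial will have an ECG and drug concentrations from the same visit, twice per patient, in a placebo-controlled design. That is nearly all a concentration-QTc analysis needs. Two things are missing: a rule placing the ECG next to a draw with both times recorded, and QTc as a named PK-PD variable. Without them the ECG conclusion rests on an arm comparison of about 30 against 30 patients, with ECGs taken at whatever point in the dosing interval the visit allows. That comparison is weak for a modest effect. Clock times not recorded at the visit may not be recoverable later.

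A second, separate matter is timing. The dog signal was present on Day 1, while the first on-drug ECG here comes at Week 6. The documents do not explain how this fits the stated focus on dog signals.

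**Working it through.** **1. The plan's own figures.** The only power figure is for dityrosine (Section 2.8.2). With a difference of (8.51 − 0.47)/2 = 4.02, SD 5.3, 30 per arm and two-sided 0.05, the t-test gives 0.823, matching the stated 0.82. The documents give no SD, effect size or power for QTc, so steps 3 to 5 rest on assumptions.

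**2. First on-drug ECG.** Day 42, or 42 − 10 = Day 32 to 42 + 10 = Day 52 if the visit variance runs both ways. This reads the baseline/Day 1 ECG as pre-dose. The Table 1 footnote supports that by letting it be merged with screening, and the Day 1 dosing list in Section 2.6.3 contains no ECG.

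**3. Arm comparison using all four on-drug ECGs (Weeks 6, 12, 18, 24).** Assumptions: 30 per arm; between-patient SD of QTc change 10 ms; within-patient SD 10 ms; between-patient exposure CV 40-60%; concentration at the ECG uniform between 0.5 and 1.5 times the patient's mean (variance 1/12); effect *d* at mean concentration, linear and without lag. For *k* ECGs per patient, the variances of a patient's mean change are:

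- placebo: 10² + 10²/k = 125 at k = 4
- active: 125 + d²CV² + d²(1 + CV²)/(12k)

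SE = √[(active + placebo)/30], tested with 58 df.

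- d = 5: active variance 129.6 (CV 40%) or 134.7 (60%); SE 2.91 or 2.94; power 0.39 either way.
- d = 7.5: 135.4 or 146.8; SE 2.95 or 3.01; power 0.71 or 0.69.
- d = 10: 143.4 or 163.8; SE 2.99 or 3.10; power 0.91 or 0.89.

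**4. Concentration-based analyses using only the Week 6 and Week 12 ECGs.** These powers come from simulation under the same assumptions, with placebo concentration set to 0. The paired analysis is a random-intercept regression of QTc change on concentration at the ECG. Null rejection was about 0.05 to 0.06.

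| Effect at mean concentration | Arm comparison, 4 ECGs | Regression on patient's mean concentration, 2 ECGs, no time-matching | Regression on concentration at the ECG, 2 ECGs |
|---|---|---|---|
| 5 ms | 0.39 | 0.42-0.51 | 0.52-0.59 |
| 7.5 ms | 0.69-0.71 | 0.76-0.83 | 0.85-0.90 |
| 10 ms | 0.89-0.91 | 0.94-0.96 | 0.98 |

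Repeat runs moved the last column by no more than about two points. An arm comparison restricted to the same two ECGs would give 0.33-0.34 at 5 ms and 0.61-0.63 at 7.5 ms. That is not a fair comparator, because Weeks 18 and 24 are also scheduled.

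**5. Sensitivity to the SD.** The assumptions in step 3 imply an SD of √(10² + 10²) = 14.1 ms for one change value. Over a wider assumed range, with correlation 0.5 between visits, the smallest difference detectable with 80% power on the mean of four visits is (1.960 + 0.842) × SD × √0.625 × √(2/30):

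| SD of one change | Detectable difference | Power, 5 ms | Power, 10 ms |
|---|---|---|---|
| 10 ms | 5.7 ms | 0.67 | 1.00 |
| 15 ms | 8.6 ms | 0.36 | 0.89 |
| 20 ms | 11.4 ms | 0.23 | 0.67 |
| 25 ms | 14.3 ms | 0.16 | 0.49 |

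A persistent 20 ms effect, the dog maximum in the 26-week study, has power 0.97 even at SD 25. A 10 ms effect only half visible at the times sampled has the power shown for 5 ms.

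**The case against.** The case for leaving the plan alone has substance.

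- **The signal is limited.** It occurred only at 500-1000 mg/kg. Section 1.3.11 reports no significant IKr activity at 300 µM and finds the animal ECG data insufficient to show a definite human risk. Phase 1 used doses up to 1800 mg and 10 days of repeat dosing, which covers the early window, though in healthy men aged 18-49. The diabetic kidney trial adds 68 patients over 12 weeks at up to 200 mg BID. All this stands and lowers the urgency.
- **The arm comparison is better than it first looks.** It has four on-drug ECGs per patient and a concurrent placebo arm. A reader might infer that a real QTc effect is likely to be missed. The documents do not support that, since they give no effect size or SD, and a persistent effect of about 10 ms or more would probably be seen unless the SD is at the high end of step 5.
- **QTc is not excluded.** Section 2.8.4 leaves the choice of secondary endpoints open, and Section 2.7.2 counts adverse events among them. QTc is unspecified rather than ruled out.
- **Concentration at the ECG is not wholly unknown.** The arrival and departure draws bracket the visit, Section 2.6.5 has research samples labelled with collection time, and a population PK model is planned. What the protocol does not require is an ECG time to set against them.
- **The power gain is flattered.** The simulation fits the model that generated its data, and about half or more of the gain over a two-ECG arm comparison comes from regressing on exposure, without any time-matching.

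What remains is that the pairing and the analysis are unspecified, and that specifying them costs almost nothing.

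**Conclusion.** The point holds as an inexpensive improvement, not as a flaw that undermines the trial. The design can probably detect a persistent QTc effect of about 10 ms or more. It may miss one of about 5 to 7.5 ms. Under the stated assumptions, two PK-paired ECGs raise power from about 0.39 to 0.52-0.59 at 5 ms, and from 0.69-0.71 to 0.85-0.90 at 7.5 ms. These are best-case figures for a linear, no-lag relation with one concentration variable, and no QTc input comes from the documents.

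The Week 6 matter is narrower. A reader might infer that an early effect will be lost. The smaller Day 23 increase in dogs makes a fading effect conceivable, but increases were still present at Week 4 at 500 mg/kg/day, and the documents give no dog-to-human exposure comparison. They support only this: the ECG schedule and the stated focus on dog signals have not been reconciled.

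**What to change.** - **Section 2.6.4, Weeks 6 and 12.** Record the already scheduled ECG next to one of the already scheduled PK draws, and capture both clock times.
- **Section 2.8.4.** Add QTc change from baseline to the PK-PD analysis, using one correction formula named in advance and applied throughout that analysis. Fit a mixed model on parent and GKT138184 concentration (placebo = 0). Report the predicted effect and confidence interval at the mean observed concentrations. Parent and metabolite slopes may be hard to separate, so this prediction is the quantity to interpret.
- **Sections 1.3.11, 2.6.4 and 5.7.3.1.** The sponsor should reconcile the absence of an on-drug ECG before Week 6 with the stated focus on dog toxicity signals. No schedule or eligibility formula is proposed here.

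The first two changes need no new visit, blood sample or ECG. Their cost is minor sequencing within two visits and one extra model, whose linear, no-lag assumption should be checked and reported.
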